6.3 RESCUE MEDICATION USE

Rescue medications will be administered in cases detailed in [section 7.2.2](#). Rescue therapy will be defined as any treatment that would have a therapeutic effect on inflammation in the anterior segment, other than the IP (e.g., systemic treatment with an immunosuppressant agent, or topical corticosteroids in the study eye), regardless of the purpose of administration and whether it was recorded as a rescue therapy on the eCRF.

Systemic immunosuppressive therapy (e.g., methotrexate, cyclosporine, cyclophosphamide, chlorambucil, mycophenolate mofetil, tacrolimus, azathioprine, or adalimumab) or other therapy considered as a rescue therapy, would be administered based on the Investigator's best judgment and only after discussion with Tarsius' Medical Director. Prior to treatment with rescue medication, the subject should answer the "Subject-Rated Ocular Pain Assessment". Only then, rescue medication can be administered and treatment will be recorded as a rescue therapy in the Medications eCRF.

6.4 MEDICATIONS NOT PERMITTED

Use of the following medication is not permitted during the study and **14** days prior to Visit 2 (Day of Surgery):

1. Any topical ophthalmic medications (either eye) other than study required medications. Note: Use of PRN artificial tears up to twice a day (BID) is allowed, and should not be dosed within 10 minutes of investigational product dosing.
2. Prostaglandins. Use of IOP lowering medications, other than prostaglandins, are allowed beginning on Day 0 and during the study, as needed. IOP lowering eye drops should be dosed at least 30 minutes before investigational product dosing.
3. Systemic NSAIDs. Occasional use (≤ 2 times per week) of Systemic NSAIDs or OTC painkillers to treat minor non-ocular conditions is acceptable. Low- dose aspirin for cardiovascular prophylaxis is allowed. Acetaminophen may be administered pre and post-operatively as needed for pain on the day of surgery.
4. Treatment with nasal, topical dermal steroids or immunosuppressants.

Use of the following medication is not permitted during the study and 30 days prior to Visit 2 (Day of Surgery):

1. Use of topical ocular therapy (both eyes) with antibiotics. Note: Antibiotic eye drops that are routinely administrated prior/during and post cataract surgery are allowed.
2. Use of systemic or ocular immunosuppressants or immunomodulators including steroids (oral, inhaled, injectable, nasal, topical dermal).
3. Use of systemic alpha-1 antagonists.
4. Any ocular, topical or systemic medication that could interfere with wound healing, the test agent, or the interpretation of study results.
5. Other investigational drugs or devices

6.5 TREATMENT COMPLIANCE

In order to obtain reliable safety and efficacy data, it is critical that each subject comply with the dosing schedule specified in the protocol.

Subjects will be instructed to record administration information from Day 1 and for the duration of the study in a dosing diary .

7 SAFETY AND EFFICACY VARIABLES

7.1 SAFETY VARIABLE

Incidence and severity of treatment-related AEs and SAEs, both systemic and ocular events.

7.2 SAFETY VARIABLES

Safety measures include AEs/SAEs and clinical assessments from the slit-lamp biomicroscopy findings, IOP, and dilated ophthalmoscopy findings.

AEs and ocular safety measures to be collected in this study are listed in [Table 4](#).

TABLE 4: OCULAR SAFETY MEASURES

Safety Measure	Note
Slit-lamp biomicroscopy: Lid hyperemia, lid edema, conjunctival hyperemia, chemosis, corneal edema, conjunctival discharge/exudate	The status of each of these biomicroscopy parameters will be rated as 0 = None, 1 = Mild, 2 = Moderate, or 3 = Severe. For each abnormal record, the clinical significance (Clinically Significant or Not Clinically Significant) will also be determined. Slit-lamp biomicroscopy will be performed at all study visits, except Visit 2 (Surgery).
Intraocular pressure	The IOP measurements will be performed by Goldmann applanation tonometry. IOP pressure recorded in mmHg (e.g., 18mmHg). IOP measurements will be performed at all study visits, except Visit 2 (Surgery).
Dilated Ophthalmoscopy: IOL (post-surgery), vitreous haze, retina vessels, macula, optic nerve, cup/disc ratio.	The status of IOL position, macula and optic nerve will be determined as Normal or Abnormal. The cup/disc ratio will be recorded with two decimal points (e.g., 0.80). Dilated ophthalmoscopy will be performed at Visit 1 (Screening) and at Visit 6 (Day 15).

Intraocular Pressure (IOP) – IOP will be measured using Goldmann Applanation Tonometry with a single measurement.

These ocular safety measures will be summarized using descriptive statistics. For continuous ocular safety measures, changes from Baseline (Day 1 / Visit 3) variables will also be summarized descriptively.

7.2.1 Adverse Events

Adverse events will be collected for subjects following signing of the ICF through the end of the study. The information will include at least a description of the event, onset date, and resolution date, as well as seriousness, severity and relation to study medication (as determined by the Investigator), location (right eye [OD], left eye [OS], both eyes [OU] or other), action taken, and outcome. All AEs will be coded using the Medical Dictionary for Regulatory Activities (MedDRA) dictionary, current version. Ocular and non-ocular AEs will be summarized separately.

Suspected adverse reactions (SARs), also known as adverse drug reactions or suspected adverse drug reactions, are AEs considered by the Investigator to be related to the study medication and included in the Investigator's Brochure.

An AE will be considered as an *ocular AE* if the Investigator selects 'OD', 'OS', or 'OU' for the AE eCRF field "Eye(s) affected".

Any AE that causes loss of vision of 15 or more letters (i.e., 3 lines) should be recorded as a serious adverse event (SAE). Examples include endophthalmitis, retinal vascular occlusion, retinal detachment involving the macula/fovea, etc. AEs that cause loss of 15 or more letters (i.e., 3 lines) that are expected to resolve should not be recorded as an SAE. Examples include corneal edema, corneal abrasion, cystoid macular edema or other conditions that are known to affect vision but expected to resolve and not results in a permanent impact on vision.

7.2.2 Criteria for Rescue Therapy

Rescue therapy will be offered if one or more of the following criteria are met and a rescue therapy treatment plan is discussed with the Tarsius Medical Director.

- [REDACTED]
- [REDACTED]
- [REDACTED]
- [REDACTED]
- [REDACTED]
- [REDACTED]

If rescue therapy is administered, the generic name, indication, route of administration, frequency, dose, start date, and stop date (if applicable) will be recorded on the eCRF. In addition, if other local therapy (i.e., periocular or intravitreal corticosteroids) is administered in the non-study eye, then the generic name, indication, route of administration, frequency, dose, start date and end date (if applicable) would also be recorded on the eCRF.

[REDACTED]

[REDACTED]

7.2.3 Other Safety Variables

Other safety measures are discussed in [section 7.2](#) above.

7.3 ADVERSE EVENT DEFINITIONS

Adverse Event (AE): Any untoward medical occurrence associated with the use of an investigational product in humans, whether or not considered drug related.

Adverse Reaction (AR): any AE caused by a drug. Adverse reactions are a subset of all suspected adverse reactions where there is reason to conclude that the drug caused the event.

Suspected Adverse Reaction (SAR):

Any AE for which there is a reasonable possibility that the drug caused the AE. For the purposes of IND safety reporting, “reasonable possibility” means there is evidence to suggest a causal relationship between the drug and the AE. A SAR implies a lesser degree of certainty about causality than adverse reaction, which means any AE caused by a drug.

Unexpected: An AE or SAR is considered “unexpected” if it is not listed in the Investigator’s Brochure or is not listed at the specificity or severity that has been observed; or, if an Investigator’s Brochure is not required or available, is not consistent with the risk information described in the general investigational plan or elsewhere in the current application.

Life-threatening: An AE or SAR is considered “life-threatening” if, in the view of either the Investigator or sponsor, its occurrence places the patient or subject at immediate risk of death. It does not include an AE or suspected adverse reaction that, had it occurred in a more severe form, might have caused death.

A SERIOUS ADVERSE EVENT (SAE) is any AE or suspected adverse reaction occurring at any dose that:

- Results in death.
- Is life-threatening.
- Results in a persistent or significant incapacity or substantial disruption of the ability to conduct normal life functions.
- Requires inpatient hospitalization.
- Prolongs inpatient hospitalization.
- Is a congenital anomaly/birth defect.
- Is a significant medical event (i.e., one that may jeopardize the subject or may require intervention to prevent one or more of the other outcomes listed above).

A NON-SERIOUS ADVERSE EVENT is any AE that does not meet the definitions for SAEs as described above.

Each **AE** will be classified as **SERIOUS or NON-SERIOUS** using the definitions provided above.

The **SEVERITY** of each AE will be classified as **MILD, MODERATE, or SEVERE**.

The Investigator will review each event and assess its **RELATIONSHIP** to use of investigational product (unrelated, probably, definitely). The AE will be assessed using the following definitions:

Unrelated:

- Event occurring before dosing.
- Event easily explained by uncomplicated cataract surgery
- Event or intercurrent illness due wholly to factors other than investigational product use.

Probable:

- Reasonable temporal relationship with investigational product use.
- Likely to be known reaction to agent or chemical group, or predicted by known pharmacology.
- Event cannot easily be explained by subject's clinical state or other factors.

Definite:

- Distinct temporal relationship with investigational product use.
- Known reaction to agent or chemical group, or predicted by known pharmacology.
- Event cannot be explained by subject's clinical state or other factors.

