7.4 PROCEDURES FOR AE REPORTING BY THE INVESTIGATOR

AEs will be monitored throughout the study and will be recorded on the CRF with the date and time of onset, date and time of resolution, severity, seriousness, causality (relationship to use of investigational product), treatment required, and the outcome.

To elicit AEs, simple questions with minimal suggestions or implications should be used as the initial questions at all evaluation points during the trial. For example:

- How have you felt since your last assessment?
- Have you had any health problems since your last assessment?

The severity of each AE should be categorized as mild, moderate, or severe.

The causality of use of investigational product in relation to the AE will be assessed by the Principal Investigator after careful medical consideration and categorized as unrelated, probable, or definite.

If an AE occurs, the Investigator will institute support and/or treat as deemed appropriate. If a non-SAE is unresolved at the time of the last day of the study, an effort will be made to follow

up until the AE is resolved or stabilized, the subject is lost to follow-up, or there is some other resolution of the event.

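### The causality scale in section 7.3 has no clear related grade for a reaction neither known nor predicted, and sections 7.2.1, 7.3 and 7.5 disagree on what counts as a suspected or possibly related event

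*Combined protocol and SAP*

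**What the plan says.** Section 7.4 has the Principal Investigator judge causality, which is to be "categorized as unrelated, probable, or definite". Section 7.3 directs that events be graded by the definitions it then lists.

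- *Probable* has three bullets: reasonable timing; "Likely to be known reaction to agent or chemical group, or predicted by known pharmacology"; and "Event cannot easily be explained by subject's clinical state or other factors".
- *Definite* has the same three in stricter form: distinct timing, a known (not merely likely known) or predicted reaction, and no possible explanation by the subject's state or other factors.
- *Unrelated* also has three: onset before dosing; "Event easily explained by uncomplicated cataract surgery"; and "Event or intercurrent illness due wholly to factors other than investigational product use".

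Neither section says whether all bullets of a grade must hold or whether one is enough.

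Suspected adverse reactions (SARs) are defined twice. Section 7.2.1 requires that the investigator judge the event related and that it appear in the Investigator's Brochure. Section 7.3 has "Any AE for which there is a reasonable possibility that the drug caused the AE". It adds that, for IND safety reporting, reasonable possibility "means there is evidence to suggest a causal relationship between the drug and the AE". Its definition of *unexpected* covers a SAR that the Brochure does not list. The note that closes section 7.5 has the sponsor notify all sites of an unexpected SAE judged related to the product, or possibly so.

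Section 7.1 names treatment-related AEs and SAEs as the safety variable. Section 9.1.2 tabulates treatment-related AEs by group, with intensity and relationship, and lists treatment-emergent AEs.

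**The concern.** The primary objective is safety, and this is an early-phase study. A reaction that nobody predicted is among the things it should be able to show. If the scale offers such an event no related grade that its own definitions support, two investigators can grade the same event differently and both can defend the choice. The treatment-related table, the only AE tabulation that section 9.1.2 specifies, then depends partly on how each investigator handles a gap in the definitions.

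The surgery bullet adds to this. Every randomized subject had cataract surgery the day before the first dose, so a surgical explanation is often at hand. Changes expected after uncomplicated surgery are already kept out of the AE count (section 3.1). The bullet therefore acts as a second surgery filter, on events already accepted as AEs.

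The two SAR definitions raise a separate question: can an event that is absent from the Brochure be a suspected reaction at all?

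**Working it through.** No arithmetic applies. The check is to run a test event through the definitions and then to set the SAR passages side by side.

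**Step 1. Test event.** It starts after dosing, has distinct timing, is neither known for the agent or its chemical group nor predicted by pharmacology, and has no other explanation.

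| Grade | Bullet 1 | Bullet 2 | Bullet 3 |
|---|---|---|---|
| Unrelated | before dosing: not met | easily explained by surgery: not met | wholly other factors: not met |
| Probable | timing: met | known or predicted: **not met** | not easily explained otherwise: met |
| Definite | timing: met | known or predicted: **not met** | not explained otherwise: met |

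**Step 2. All bullets required.** *Probable* and *definite* both fail on bullet 2, and *unrelated* fails on every bullet. The event has no grade. This is the natural reading, because the bullets of the two related grades run in parallel and tighten together (reasonable to distinct, likely known to known, not easily to not at all), as cumulative criteria do.

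**Step 3. Any one bullet enough.** The test event now qualifies as *probable*. But reasonable timing alone also makes an event *probable* when surgery easily explains it, and that same event is *unrelated*. This reading closes the gap only by making the grades overlap.

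**Step 4. The *unrelated* bullets.** These make sense only as alternatives, since an event before dosing and an intercurrent illness need not coincide. The surgery bullet is therefore sufficient by itself. The *wholly* test stands in the next bullet and does not qualify the surgery bullet, so an event to which the product may have contributed can still be *unrelated*.

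**Step 5. SAR definitions.**

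| | Section 7.2.1 | Section 7.3 |
|---|---|---|
| Test | judged related and in the Brochure | reasonable possibility of causation |
| Unlisted event | cannot be a SAR | can be an unexpected SAR |
| Link to adverse reaction | treated as a synonym | adverse reactions are a subset of SARs |

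An unlisted, suspected reaction is a SAR under one section and cannot be under the other. This conflict does not depend on how the grading bullets combine.

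**Step 6. Section 7.5 note.** Its trigger includes a possibly-related level. The scale has three grades, and none of them is that.

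**The case against.** The strongest reply is that section 7.4 leaves the choice to the Principal Investigator's medical judgement. The test event meets two of three *probable* bullets and no *unrelated* bullet, so a sensible investigator may well choose *probable*, which would keep it in the related table. That stands as a possible outcome, and the plan does not force such an event out. But section 7.3 tells the investigator to grade by its definitions, and on the natural reading they do not support that choice. The result then depends on the individual investigator.

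The gap is also narrow. The bullets accept a reaction known for the chemical group or predicted by pharmacology, so only a reaction that fails both tests is affected. An event that surgery could explain, but not easily, can still be *probable* if the other bullets hold.

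A reader might infer that new reactions would vanish from the safety data. The documents do not support that:

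- Section 3.1 names treatment-emergent AEs alongside treatment-related ones, and 9.1.2 lists them by group.
- Section 7.2.1 has ocular and non-ocular AEs summarized without reference to relatedness.
- Section 7.5 sends every SAE to the sponsor within 24 hours, whatever its grade.
- Ocular signs, intraocular pressure and visual acuity are summarized whatever their cause (sections 7.2 and 9.1.2).

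Nor do the documents show that site notification would fail. The section 7.5 note does not say that its judgement must use the investigator's grade; the terms simply do not match. The SAR conflict has no shown effect on analysis, since 9.1.2 tabulates treatment-related AEs and not SARs. Finally, section 9.1 refers to a statistical analysis plan whose text is not reproduced here. That plan may state which grades count as treatment-related, but it could not settle how investigators combine the bullets when they grade.

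**Conclusion.** The point holds in a limited form. The causality definitions are neither clearly complete nor clearly exclusive. On the natural reading, a reaction that is neither known nor predicted fits no grade. An easy surgical explanation suffices for *unrelated* even where the product may have contributed. Sections 7.2.1 and 7.3 contradict each other on unlisted SARs, and the section 7.5 note uses a level that the scale lacks.

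The effect is confined to the treatment-related AE variable (7.1), its table (9.1.2) and the SAR definition. How many events would be misgraded cannot be estimated, because the documents give no event frequencies and investigators may resolve the gap in either direction. The grading conclusion rests on reading the related-grade bullets as cumulative and the *unrelated* bullets as alternatives; the SAR conflict rests on neither assumption. Because safety is the primary objective and the remedy is wording, this should be corrected, though it does not compromise the safety data as a whole.

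**What to change.** In section 7.3:

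- State how the bullets of each grade combine.
- Make a known or predicted reaction supportive, not required, for *probable* and *definite*.
- Apply the *wholly* test to the surgery bullet.
- State which grades count as treatment-related.

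Use the same terms in section 7.4 and in the note that closes section 7.5. In section 7.2.1, delete the condition that a SAR be in the Investigator's Brochure, so that 7.3 governs, and bring the synonym for adverse drug reaction into line with 7.3.

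The reasonable-possibility wording in 7.3 is explained there for IND safety reporting. If the sponsor wants it as the threshold for grading every AE, the protocol should say so.

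Cost: a protocol amendment with IRB review (section 13) and investigator guidance on the revised definitions. No visit, sample-size or treatment change follows. The downside is that somewhat more AEs may be graded related in all arms, vehicle included, so the treatment-related table must be read against vehicle.

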7.4 PROCEDURES FOR AE REPORTING BY THE INVESTIGATOR

AEs will be monitored throughout the study and will be recorded on the CRF with the date and time of onset, date and time of resolution, severity, seriousness, causality (relationship to use of investigational product), treatment required, and the outcome.

To elicit AEs, simple questions with minimal suggestions or implications should be used as the initial questions at all evaluation points during the trial. For example:

- How have you felt since your last assessment?
- Have you had any health problems since your last assessment?

The severity of each AE should be categorized as mild, moderate, or severe.

The causality of use of investigational product in relation to the AE will be assessed by the Principal Investigator after careful medical consideration and categorized as unrelated, probable, or definite.

If an AE occurs, the Investigator will institute support and/or treat as deemed appropriate. If a non-SAE is unresolved at the time of the last day of the study, an effort will be made to follow

up until the AE is resolved or stabilized, the subject is lost to follow-up, or there is some other resolution of the event.

7.5 SERIOUS ADVERSE EVENT REPORTING BY THE INVESTIGATOR

Serious Adverse Event Reporting

It is the responsibility of the Investigators or their designees to report any event of this nature to the sponsor or a designee within 24 hours of the event being brought to the Investigators' or their staffs' attention. It is also the responsibility of the Investigator to report all SAEs reported at their site to their Institutional Review Board (IRB), as required. The Investigator should make every attempt to follow all SAEs to resolution.

The following information should be provided when an SAE is reported to the sponsor or designee:

1. Protocol Number
1. Site Number
2. Subject Number
3. Subject Demographic information, including:
 - Date of Birth
 - Sex
 - Race
4. Investigational product start date
5. Date of last dose of investigational product
6. Date investigational product reinitiated (if investigational product interrupted)
7. SAE information, including:
 - SAE term (diagnosis only; if known or serious signs/symptoms)
 - Description of SAE/narrative
 - Date/time of onset
 - Severity
 - Outcome
 - Date/time of resolution or death (if duration < 24 hours)
 - Relationship to investigational product
 - Action taken with investigational product
8. Criteria for classifying the event as serious, including whether the SAE:
 - Resulted in death.
 - Was life-threatening
 - Required inpatient hospitalization.
 - Prolonged inpatient hospitalization.
 - Resulted in a persistent or significant incapacity or substantial disruption of the ability to conduct normal life functions.
 - Was a congenital anomaly/birth defect

- Important medical events that may not result in death, were not life-threatening, or did not require hospitalization may be considered serious when, based upon appropriate medical judgment, they may jeopardize the patient or subject and may require medical or surgical intervention to prevent one of the outcomes listed in this definition. Examples of such medical events include allergic bronchospasm requiring intensive treatment in an emergency room or at home, blood dyscrasias or convulsions that do not result in inpatient hospitalization, or the development of drug dependency or drug abuse.

9. Concomitant medications

10. Relevant history

11. Possible causes of SAE other than investigational product

12. Copy of AE page from the CRF

NOTE: If an SAE occurs in any study involving TRS01 that is unexpected and is determined to be related or possibly related to investigational product, all sites will be notified by the sponsor and each site should report it to its IRB.

